2.6 Main Study Secondary Endpoints

Disease control

- Rates of positive biopsy for any cancer and significant cancer defined by a number of different thresholds on biopsy following focal therapy (treated and untreated side).
- Rates of second or third focal therapy sessions, in-field or out-of-field.
- Rates of radiotherapy as adjuvant or salvage therapy following surgery or focal therapy.
- Rates of prostatectomy as adjuvant or salvage therapy following radiotherapy or focal therapy.
- Rates of systemic therapy as adjuvant or salvage therapy following surgery, radiotherapy or focal therapy.
- Rates of prostate cancer-specific mortality.

IP4 - CHRONOS 19CX5006 Imperial College London Date: 13th July 2022	Short Title: IP4 - CHRONOS	Protocol No: 19CX5006	Sponsor: Imperial College London	
---	-------------------------------	--------------------------	-------------------------------------	--

- Rates of all cause mortality.
- Long-term health outcomes of those participants consenting to longitudinal follow-up will be reported in subsequent studies pending further funding.

Adverse events and functional outcomes

- Rates of cystoscopic interventions following treatment.
- Rates of implant insertion for treatment of incontinence and erectile dysfunction.
- Rates of medication and/or pump devices used for erectile dysfunction following treatment.
- Rates of endoscopic investigations of the lower bowel following treatment.
- Rates of pad-use and quantity per day for urinary incontinence following treatment.
- Rates of pad-use and quantity per day for faecal incontinence following treatment.
- Rates of adverse event rates and complications.
- Genito-urinary & rectal side-effects using patient-reported outcome measures using validated questionnaires (EQ-5D-5L, International Index of Erectile Function-15, EPIC-26, EPIC Urinary domain, International Prostate Symptom Score and CTCAEv4.0 bowel domain) including evaluation of return to baseline function for erectile and urinary function and various minimum decreases in PROMS scores as defined for IIEF and IPSS in the literature that might be clinically relevant.

Health economics

- To establish the NHS costs of the different interventions.
- The incremental cost per quality adjusted life year (QALYs) gained over the estimated lifetime of participants for focal therapy versus radical therapy.

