2.7 Summary Table of Objectives and Endpoints

Protocol No: 19CX5006 v5.0 13th July 2022

Short Title:	Protocol No:	Sponsor:	Version: 5.0
IP4 - CHRONOS	19CX5006	Imperial College London	Date:
			13 th July 2022

Study stage	Objectives	Endpoints	Time-point(s) of evaluation of this endpoint (if applicable)
Pilot	Primary	As above	At time of consent (acceptance to randomisation) and at time to treatment (compliance)
Pilot	Secondary	As above	At time of consultation for study, after consent and after treatment with a minimum follow-up of 3 months after randomisation
Main (if funded)	Primary	As above	At time of progression or failure judged clinically or maximum 5 years follow-up after randomisation
Main (if funded)	Secondary	As above	Up to and including 5 years from randomisation

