5.7 Visit Schedule

The design and number of visits mirror the standard of care pathway for patients undergoing either focal therapy or radical therapy, so that additional patient burden is minimal. Prior to enrolment, all patients will have undergone a Prostate Specific Antigen (PSA) blood test, a diagnostic prostate MRI and prostate biopsies. A standard of care (SOC) multi-disciplinary team case review will precede any discussion with the patient on all suitable treatment options and trial suitability. After an MDT discussion confirming suitability for FT and/or radical therapy has taken place, a patient information sheet (PIS) explaining the study will be provided, after which patients will be given a minimum of 24 hours to consider taking part. We aim for consent to be taken during a SOC appointment, or an additional consultation via phone, or in person. Randomisation will take place during the visit in which consent is taken along with any required neoadjuvant therapy, as allocated via randomisation, to be prescribed and within 24 hours of receiving the prescription. Time from randomisation will be used to define progression free survival and failure free survival. The end of treatment is defined as the final part of any intervention. For radiotherapy, this is the final radiation fraction completed and for prostatectomy and focal therapy the point at which the catheter is removed. Therefore, the follow-up visits noted below will start from these time-points, which will define the date of first follow-up visit (visit 2).

Protocol No: 19CX5006 v5.0 13th July 2022

IP4 - CHRONOS 19CX5006 Imperial College London Date: 13 th July 2022

Visit Schedule:

	Screening & Consent	Visit						
Visit	1	2	3	4	5	6	7	6 monthly visits until last visit 60 months after visit 2
Months		These below specify the months after the completion of each treatment in each arm						
		0	3	12	18	24	30	31-60. Visits 4 onwards can be telephone consultations in order t note clinical outcomes although MRI scans and biopsies where done will require physical visits to the hospital
Informed Consent and enrolment into either CHRONOS A or CHRONOS B	Х							
Inclusion & exclusion criteria checked, including concomitant medication review	Х							
Randomisation	Х							
Prescription of neo- adjuvant therapy	X (if randomised to such arm)							Within 24hrs of randomisation
PSA blood test	Such anny		Х	Х	Х	Х	Х	X (6 monthly)

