Prostate Contrast MRI	X (if randomised to focal therapy and no contrast given during diagnostic scan – to have prior to visit 2)							
Prostate mpMRI				X (focal therapy arms)				
Biopsy (optional)				X (focal therapy arms)				
Treatment		X (these vary in length)		,				X (focal therapy arms – a second treatment will be permitted for a histologically confirmed recurrent residual or new out-of-field disease)
Clinical assessment (optional, only if required)			X	Х	X	X	X	
PROMS questionnaires	Х		Х	Х		Х		X (every 12 months, at 24, 36, 48 and 60 months visits)
Review/ reporting of patient AEs/SAEs		X	Х	Х	X	X	Х	X
Blood and urine tests including those for	Х		Х	Х				Х

Short Title:	Protocol No:	Sponsor:	Version: 5.0
IP4 - CHRONOS	19CX5006	Imperial College London	Date:
			13 th July 2022

biobanking (optional)				

Time window for each visit will be +/- 4 weeks

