5.9 Follow-up

Follow-up will consist of serum Prostate Specific Antigen (PSA) tests at 3 months and 12 months after completion of treatment as defined above. Thereafter, PSA will be measured 6-monthly until a progression event is determined, for 5 years after initial randomisation or mortality (whichever is first).

Patient reported outcome measures (PROMs) will be collected at 3 and 12 months and then annually thereafter until progression, mortality or 5 years after initial randomisation (whichever is first). The minimum follow-up for each patient will be 5 years in the main study although yearly follow-up will continue long term in clinical standard care through linkage to national databases.

NB: if the trial does not proceed to the Main Stage following the analysis of the Pilot, patients will be followed up for a minimum of 3 months and will then revert to standard of care in which the clinical care provided to patients will not differ from the clinical follow-up stipulated in this protocol. At the end of the study patients will continue to be followed up locally within their recruitment centres within the ICE (European Registry for Cryosurgical Ablation of the prostate, EuCAP) or the HEAT international HIFU registry as per NICE guidelines IPG432/IPG42.

Patient reported outcome measures

The EORTC QLQ-C30 with the prostate-specific module, International Prostatic Symptoms Score (IPSS), EPIC bowel and bladder and International Index of Erectile Function 15 (IIEF15) will be used.

The EuroQol (EQ-5D) will be used in the study as a generic measure of health-related quality-of-life which can be linked to public preferences. These data will be used to calculate quality-adjusted life-years as part of a future health economic evaluation. Patients agreeing to return questionnaires on quality of life should continue to complete quality of life data for 5 years after randomisation. Questionnaires should be self-administered, although it is recommended that a key person (e.g. research nurse) at each centre be responsible for the data collection to optimise compliance and completeness of the data.

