Based on an allocation ratio of 1:1 and a non-inferiority margin of 0.05 with a 0.85 PFS rate in the standard care arm (at median 5-years), power 0.80 and alpha 0.05, drop-out after randomisation of 5%, the overall required sample size is 1190 with 136 expected total number of events. Total recruitment and follow-up period will be 8 years. If recruitment rates were deemed to be high then the power could be adjusted to 0.90 and the total sample size will be 1660 with 189 expected total number of events. This will be on the advisement of the TSC. PFS for the main Stage will be defined as transition to salvage therapies or metastases or mortality related to prostate cancer.

CHRONOS-B main stages II and III: Using the latest update of –nstage-, with an allocation ratio of 1:1:1, we anticipate approximately 1200 patients are required over 5 years to observe 120 control arm failure-free survival (FFS) events within 7.6 years. This time will be dependent on observed FFS event rates and is based on an assumption of 20 patients recruited per month. This calculation gives 85% power at the efficacy stage analysis, to detect a hazard ratio (HR) of 0.67 and is based on 20% of patients having a FFS event by 3 years (30% by 5-years).

Table 1. Sample size calculations

	Short Title: IP4 - CHRONOS	Protocol No: 19CX5006	Sponsor: Imperial College London	Version: 5.0 Date: 13 th July 2022
١				10 Gary Lore

	Stage 1	Stage 2	Overall
Alpha	0.45	0.025	0.044
Power	95%	85%	83%
Critical HR (guidance for stopping early)	0.974		-
Control Arm Events	47	120	-
Accrual	20pts/m	20pts/m	20pts/m
Cumulative Patients	1003	1200	-
Time to analysis (years)	3.4	4.2	7.6

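### Protocol section 5.9 gives two incompatible rules for how long PROMs are collected; one of them stops collection at progression

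*Protocol*

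**What the plan says.** Four places in the protocol bear on PROM duration in the main stage.

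- **Section 5.9, second paragraph.** PROMs are collected at 3 and 12 months and then "annually thereafter until progression, mortality or 5 years after initial randomisation (whichever is first").
- **Section 5.9, patient reported outcome measures.** "Patients agreeing to return questionnaires on quality of life should continue to complete quality of life data for 5 years after randomisation". No stop at progression is mentioned.
- **Section 5.7, visit schedule, PROM row.** "X (every 12 months, at 24, 36, 48 and 60 months visits"), again with no stop. The schedule counts months from the end of treatment: "6 monthly visits until last visit 60 months after visit 2".
- **Section 2.7, objectives table.** Main-study secondary endpoints are evaluated "Up to and including 5 years from randomisation".

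The PROMs support a named secondary endpoint in section 2.6, "including evaluation of return to baseline function for erectile and urinary function". EQ-5D supplies the QALYs (5.9), which section 2.6 wants over the estimated lifetime.

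The event definitions decide whose forms would stop. In CHRONOS-A (2.5, 5.9) progression is salvage local or systemic therapy, metastases, prostate cancer death or, after radical therapy only, biochemical failure. Biochemical failure counts even if no salvage is given. Repeat focal therapy becomes salvage at the third session. In CHRONOS-B (2.5) one further focal session is already an event, but that event is called failure, not progression.

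**The concern.** The two statements in 5.9 cannot both be followed for a man who has had an event. One site could stop his questionnaires and another could continue them, each complying with the protocol.

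The early stop would also fall at an awkward moment. Salvage surgery, radiotherapy and systemic therapy are themselves PFS events, so questionnaires would end as a treatment that may affect function begins. Section 8.1.2 argues for CHRONOS-A on the basis of non-inferior PFS with fewer side-effects, and PROMs are the main measure of the second half of that argument. Whether a form is collected would depend on the primary outcome. It could also depend on the arm, because biochemical failure ends collection only after radical therapy. Forms that were never sent out cannot be recovered later.

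**Working it through.** **1. The texts side by side**

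| Place | End of PROM collection | Stop at progression? | Time origin |
|---|---|---|---|
| 5.9, second paragraph | earliest of progression, death, 5 years | yes | randomisation |
| 5.9, PROM paragraph | 5 years | none stated | randomisation |
| 5.7, schedule | 60 months | none stated | visit 2 (end of treatment) |
| 2.7, table | 5 years | none stated | randomisation |

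The direct contradiction is between the two statements in 5.9. The schedule and the table are silent on progression; they do not state the opposite.

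The time origins conflict as well. In the CHRONOS-B drug arms focal therapy follows 12 weeks (84 days) of drug, so the 60-month form is due at least 84 days after the 5-year point from randomisation. With the 4-week (28-day) window, the earliest it can fall is 84 − 28 = 56 days after that point.

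**2. Check on the CHRONOS-B event rate**

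The sample size in 8.1.2 "is based on 20% of patients having a FFS event by 3 years (30% by 5-years"), with about 120 control events by 7.6 years. Assume exponential times, 400 control men (3.2) and uniform accrual over 5 years.

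- Hazard: h = −ln(0.70)/5 = 0.0713 per year.
- Follow-up at 7.6 years runs from 2.6 to 7.6 years, so mean survival = [exp(−2.6h) − exp(−7.6h)]/(5h).
- Expected control events = 400 × (1 − mean survival) = 120.5, which agrees with the stated 120.

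**3. Men whose PROMs would stop by 5 years under the first rule**

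- CHRONOS-A at 85% PFS: 1 − 0.85 = 15%; 0.15 × 595 ≈ 89 men per arm.
- CHRONOS-A at the margin: 1 − (0.85 − 0.05) = 20%; 0.20 × 595 = 119 men.
- CHRONOS-B control, *if FFS failure counts as progression*: 30%; 0.30 × 400 = 120 men.
- CHRONOS-B drug arm at HR 0.67, same reading: 1 − 0.70^0.67 = 21.3%; 0.213 × 400 ≈ 85 men.

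**4. Share of annual forms not collected**

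For forms at years t = 1 to 5 from randomisation, the share lost at year t is 1 − exp(−ht). This applies the stop to the 12-month form too.

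| Group | Year 1 | 2 | 3 | 4 | 5 | Mean |
|---|---|---|---|---|---|---|
| A, 85% PFS | 3.2% | 6.3% | 9.3% | 12.2% | 15.0% | 9.2% |
| A, 80% PFS | 4.4% | 8.5% | 12.5% | 16.3% | 20.0% | 12.4% |
| B control | 6.9% | 13.3% | 19.3% | 24.8% | 30.0% | 18.9% |
| B drug, HR 0.67 | 4.7% | 9.1% | 13.4% | 17.4% | 21.3% | 13.2% |

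These figures include the few men whose event is prostate cancer death, for whom collection ends under any rule. Section 1.1 puts cancer-specific survival after focal therapy above 99% at 5 years.

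**The case against.** The strongest reply is that, on balance, the protocol favours continued collection. One explicit sentence in 5.9, the schedule and the objectives table all point to 5 years, against one sentence for the early stop. A reader might infer that function after failure will never be measured. The documents do not support that, because it holds only if the first sentence prevails, and they do not say that it does. The reply does not remove the problem: the words requiring the earliest of the three end-points are explicit, and a site can follow them.

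Three further objections stand.

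- **Second focal session in CHRONOS-A.** A reader might infer that function after any repeat focal treatment is lost. Section 5.9 says a second session in CHRONOS-A is not failure, so PROMs continue after it even under the strict rule. The exception is contralateral hemiablation after hemiablation, which 5.8 calls failure.
- **The word progression in CHRONOS-B.** Sections 2.7 and 8.3 keep progression and failure apart. The 30% and 21% therefore rest on a reading that the protocol does not state.
- **What is still collected.** Men contribute PROMs up to their event, so it would be wrong to say that the comparisons describe only men whose first treatment worked. That concern is confined to late time points. Adverse events and rates of implants, erectile medication and cystoscopic procedures are recorded separately (2.6, 5.7). These do not replace the questionnaires or EQ-5D.

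Missing-data methods are deferred to a statistical analysis plan (8.3). The SAP supplied covers feasibility only and specifies none (SAP 9.6), so nothing yet offsets the loss.

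**Conclusion.** The point holds as an internal contradiction with a real consequence if it is resolved the wrong way. Under the first rule, about 15% of CHRONOS-A men at 85% PFS, and 20% at the margin, would have no PROM or EQ-5D data after their event. In CHRONOS-B the corresponding figures are about 30% of controls and 21% at HR 0.67, conditional on progression meaning FFS failure. The 5-year proportions use the plan's own event rates, plus proportional hazards for the drug arm. The form shares also assume exponential times.

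Truncation would depend on outcome. It could differ by arm in CHRONOS-A because sections 2.5 and 5.9 count biochemical failure only after radical therapy; the shorter PFS definitions in 2.2 and 8.1.2 do not list it.

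The size and direction of any bias in function or QALYs cannot be derived from the documents. A reader might take the quoted rates and calculate an understated erectile dysfunction rate after focal therapy: 10% in men not salvaged, 10% salvaged and 30–60% dysfunction after salvage give 0.9 × 10% + 0.1 × 30% = 12%, up to 0.9 × 10% + 0.1 × 60% = 15%. That result follows only from its inputs. The 30–60% is the rate for primary radical surgery, the 10% needing further treatment includes systemic therapy (1.1), and failures in the radical arm would be truncated too.

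This is an important correction before the main stage, which is conditional on funding. PROMs are secondary outcomes. The primary endpoints, the sample sizes and the pilot decision are untouched, and pilot PROMs are collected at screening and 3 months only (SAP 9.4). Pilot men do carry over into the main stage (8.1.1), so the rule should be settled before their later forms fall due.

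**What to change.** Before the main stage:

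1. In section 5.9, delete progression from the PROM stopping rule. PROMs and EQ-5D then continue after any PFS or FFS event until death, withdrawal or the final scheduled PROM visit. This also removes the question of whether progression covers FFS failure.
2. Choose one time origin for PROMs and use it in sections 2.7, 5.7 and 5.9, so that the last form is not both required at 60 months after visit 2 and excluded at 5 years after randomisation.
3. State in the protocol and in the main-stage SAP that functional and QALY comparisons use all randomised men, including data collected after an event.

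The cost is a few edited sentences and some additional questionnaires from men who have had an event. The visits are already in the schedule, and section 5.9 already allows return by post or electronically.

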5.8 Treatment

CHRONOS-A

- Arm 1 (Control arm): Radical therapy (prostatectomy or radiotherapy [external beam or brachytherapy]). The type of radical therapy will be determined by physician or patient preference.
 - In radiotherapy patients, neoadjuvant ADT permitted and if given, minimum 3 months and maximum 6 months duration.
 - We anticipate lymph node treatment in this group is not required but 'for cause lymph node treatment will be permissible if strong clinical preference is demonstrated.
 - If an extended lymph node dissection is anticipated this will need to be discussed in a central review by the surgery subgroup.
 - As per Radiotherapy Trials Quality Assurance (RTTQA) centres and physicians delivering radiotherapy will need to be approved.
 - o Radiotherapy detailed protocols will be set out in a separate SOP.
 - Surgeons and surgical centres currently are approved as a national commissioning programme so any centre or surgeon permitted to carry out radical prostatectomy in standard NHS practice will be permitted to deliver prostatectomy within this trial.
 - o Prostatectomy details will be set out in a separate SOP.
- Arm 2 (Intervention arm): Focal therapy alone (high intensity focused ultrasound [HIFU] or cryotherapy or other validated energy modality as per physician/patient decision/choice. Other energy modality will only be added after TSC and TMG approval and a substantial amendment approved by all required bodies.
 - A second treatment either in-field or out-of-field will be permitted either after the MRI and optional biopsy showing clinically significant cancer at 12-months or due to suspicion of residual or new contralateral disease at a future date with a positive biopsy for clinically significant cancer.
 - Cryotherapy can be used after HIFU and HIFU can be used after cryotherapy.
 This second focal therapy session will be part of the focal therapy intervention
 - Where patients have undergone hemiablation to one lobe and then undergo hemiablation of the contralateral lobe will be designated as failure of focal therapy
 - Focal therapy details will be set out in a separate SOP.

Patients previously or currently on 5 alpha reductase inhibitors or anti-androgens, or LHRH agonists or LHRH antagonists are still eligible for CHRONOS A.

CHRONOS-B

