 Arm 1 (Control arm): Focal therapy alone (high intensity focused ultrasound [HIFU] or cryotherapy or other validated energy modality as per physician and centre choice). A second treatment in-field, or a first focal ablation to an out-of-field progressive or de novo lesion will be allowed but will be regarded as failure events for the purpose of CHRONOS-B. Cryotherapy can be used after HIFU and HIFU can be used after

Short Title: IP4 - CHRONOS	Protocol No: 19CX5006	Sponsor: Imperial College London	Version: 5.0 Date: 13 th July 2022
			10 daily 2022

cryotherapy. Where patients have undergone hemiablation to one lobe and then undergo hemiablation of the contralateral lobe will be designated as failure of focal therapy

- Arm 2 (Intervention arm): Neoadjuvant finasteride 5mg once daily for a minimum of 12 weeks (84 days) followed by focal therapy (as per control arm).
- Arm 3 (Intervention arm): Neoadjuvant bicalutamide 50mg once daily therapy for 12 weeks (84 days) followed by focal therapy (as per control arm).

Other arms can be added in future with protocol amendments.

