- As there is no defined time-point for a PSA nadir value following FT the PSA value at 12-months post randomisation in patients with a negative MRI will be used. Following this if there are any two further consecutive rises in PSA at least 3 months apart, with no influencing factors at the time (e.g., urinary tract infection, instrumentation/procedures, biopsies, catheterisation), a for-cause mpMRI with or without biopsies can be carried out at the discretion of the treating clinician. The Focal Therapy Sub-Group should be informed of this and a review of the for-cause mpMRI findings prior to biopsy should be carried out. Clinically significant prostate cancer in-field that is suitable for further FT should be offered to patients as a routine. Radical therapy should be only recommended to patients in instances where further FT is not suitable. Such situations should only occur after the Focal Therapy Subgroup has reviewed the case as expertise for such decisions may not reside in the local centre.
- In CHRONOS A, a second treatment either in-field or out-of-field will not be classified as failure and is part of the overall focal therapy intervention. In patients who undergo a second treatment of FT the nadir value will be defined at the 12-month time point after the second treatment, provided mpMRI and biopsy targeted at treated area(s) are negative for clinically significant prostate cancer.

Radiotherapy/ Brachytherapy

 In patients where there is suspected PSA relapse but the international definition of biochemical failure (PSA nadir plus 2.0ng/ml) has not been reached, evaluation should include a for-cause mpMRI and biopsy if required. Staging scans should be done as

Short Title: IP4 - CHRONOS	Protocol No: 19CX5006	Sponsor: Imperial College London	Version: 5.0 Date: 13 th July 2022
			10 daily 2022

per local practice. Where salvage local or systemic therapy is given, this will be regarded as PFS event.

Surgery

- Adjuvant or salvage radiotherapy will be regarded as a PFS event and will be determined based on histological findings and PSA kinetics even if the biochemical failure definition is not reached (PSA >/=0.2ng/ml). Staging scans should be done as per local practice.
- Biochemical failure following radical therapy as internationally defined, even if salvage therapy is not given, will be counted as an event for PFS/FFS analyses.

Collection of postcodes

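### The reference PSA after first focal therapy is dated from randomisation, but the PSA and mpMRI that supply it are timed from treatment; for CHRONOS-B drug-arm men who complete the lead-in, the scheduled scan cannot fall on the stated date

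*Protocol*

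**What the plan says.** Protocol 5.9, under the focal therapy heading, notes that no time-point for a PSA nadir is established after focal therapy and supplies one: "the PSA value at 12-months post randomisation in patients with a negative MRI will be used". Two later consecutive rises, at least three months apart and without another explanation, then allow the treating clinician to order a for-cause mpMRI.

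The tests that would supply this value are timed differently:

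- **PSA.** Protocol 5.9 states: "Follow-up will consist of serum Prostate Specific Antigen (PSA) tests at 3 months and 12 months after completion of treatment as defined above". Completion is defined in Protocol 5.7 as "for prostatectomy and focal therapy the point at which the catheter is removed".
- **mpMRI.** The same section schedules one scan in the focal arms, 12 months after focal therapy. Under further follow-up imaging it says that no other follow-up imaging is protocol-led.
- **Visit 4.** In the Protocol 5.7 table, this visit (12 months after treatment) is where PSA and mpMRI coincide. The tolerance is given as "Time window for each visit will be +/- 4 weeks".
- **Second session.** For a man re-treated in CHRONOS-A, the next rule in 5.9 takes the nadir 12 months after the second treatment.

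In CHRONOS-B the drug arms have a lead-in before focal therapy. Protocol 5.8 gives the finasteride arm as "Neoadjuvant finasteride 5mg once daily for a minimum of 12 weeks (84 days) followed by focal therapy (as per control arm"). The bicalutamide arm also has 84 days, and Protocol 6.1 makes this a minimum for both drugs. Protocol 6.4 has the drug dispensed within 24 hours of randomisation.

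**The concern.** One rule uses two clocks, and nothing in either document reconciles them. The reference value is fixed on the randomisation clock, but its qualifying condition (a negative MRI) depends on a scan fixed on the treatment clock. The longer the gap between randomisation and focal therapy, the further apart the two dates fall. In the drug arms the protocol itself builds in a gap of at least 84 days.

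What is at stake is the start of the two-rise count. That count can lead to a for-cause mpMRI, then a biopsy, then a further focal session. In CHRONOS-B a further session counts against the arm: Protocol 5.8 says such treatments "will be allowed but will be regarded as failure events for the purpose of CHRONOS-B". If sites resolve the conflict in different ways, men will have baselines taken at different times since ablation.

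**Working it through.** The only related conversion in the plan is 12 weeks to days, and it checks: 12 × 7 = 84. The rest is calendar arithmetic.

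**Inputs.** Day 0 is randomisation. Twelve months = 365.25 days, one month = 30.44 days, and the visit window is ±28 days (Protocol 5.7). T is the number of days from randomisation to completed focal therapy. The drug is not dispensed before randomisation, so T is at least 84 for a man who completes the lead-in.

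**Formulas.**

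- Stated reference date: day 365.25.
- Visit 3 (3-month PSA): T + 91.3 ± 28.
- Visit 4 (PSA and mpMRI): T + 365.25 ± 28.
- Visit 4 includes day 365.25 if T ≤ 28. It overlaps 365.25 ± 28 if T ≤ 56.
- Months since completed focal therapy at the stated date: (365.25 − T) / 30.44.

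| T (days) | Visit 3 PSA | Visit 4 PSA + mpMRI | Stated date inside visit 4? | Overlap with ±28 on both? | Months since focal therapy at stated date |
|---|---|---|---|---|---|
| 0 | 63–119 | 337–393 | yes | yes | 12.0 |
| 28 | 91–147 | 365–421 | yes, at the edge | yes | 11.1 |
| 56 | 119–175 | 393–449 | no | yes, at the edge | 10.2 |
| 84 | 147–203 | 421–477 | no | no | 9.2 |
| 112 | 175–231 | 449–505 | no | no | 8.3 |

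**Drug-arm men completing the lead-in.** At T = 84 the visit 4 window opens at 84 + 365.25 − 28 = 421.25. The gap to the stated date is 421.25 − 365.25 = 56 days. With ±28 days on both dates it is 421.25 − 393.25 = 28 days. A longer wait widens both gaps.

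**Could a scheduled PSA fall there instead?** The visit 3 window contains day 365.25 only if T lies between 365.25 − 91.3 − 28 = 246 and 365.25 − 91.3 + 28 = 302 days, which is 8.1 to 9.9 months. With tolerance on both dates the range is 218 to 330 days, or 7.2 to 10.8 months. No PSA is scheduled between visits 3 and 4.

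**Focal-alone men.** The dates part company if T exceeds 28 days, or 56 with tolerance on both. Neither document gives this wait; SAP 8.3 only plans to record it.

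**Share of patients (Protocol 3.2).** Drug arms 2 × 400 = 800; all focal-therapy patients 595 + 3 × 400 = 1,795; 800 / 1,795 = 44.6%. Using the 1,260 total in Protocol 8.1.1 and assuming equal arms of 420, the share is 840 / 1,855 = 45.3%.

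**The case against.** The strongest reply is that context supplies the intended meaning. The rule sits just after the scheduling of the 12-month post-treatment mpMRI, requires a negative MRI, and is followed by a second-session rule on the treatment clock. Visit 4 is the only scheduled visit with both tests, so most sites would probably use it. This makes a drafting slip likely. It does not remove the error: a site that uses visit 4 departs from the text, and a site that follows the text must add a test.

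A second reply is that the words can be met. An unscheduled PSA at 12 months after randomisation could be qualified later by a negative visit 4 scan. That is true, but for men who complete the lead-in the sample would be taken at most 9.2 months after ablation.

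A third reply is that little depends on the value, and this largely stands. The value is not a PFS or FFS event (Protocol 2.5), and Protocol 5.9 says focal therapy has no validated definition of biochemical failure. The for-cause scan is discretionary. Protocol 5.9 separately recommends imaging when PSA rises, and Protocol 5.8 allows a second CHRONOS-A session "due to suspicion of residual or new contralateral disease at a future date with a positive biopsy for clinically significant cancer". Every focal arm keeps its scheduled 12-month mpMRI, and the feasibility SAP does not use the value.

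A reader might infer that baselines differ by arm and so bias the CHRONOS-B comparison. The documents do not support that. Focal-alone men treated within 28 days would have a baseline 11.1 to 12.0 months after treatment, but their actual wait is not given. If they too waited about 84 days, the baselines would align. A between-arm difference is possible but not shown.

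**Conclusion.** The rule is wrong as written and should be corrected. For CHRONOS-B drug-arm men who complete the 84-day lead-in, no scheduled mpMRI falls on the stated date, and no scheduled PSA does unless focal therapy is delayed to about 8 to 10 months. This rests only on the lead-in, the visit schedule and the visit window, and it survives giving the tolerance to both dates.

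The figure of 800 of 1,795 is an upper bound. It assumes that every drug-arm man completes the lead-in and has a negative MRI, and that neither arm closes at the interim analysis. It also presupposes that the main stage is funded. It should not be read as the number who would receive a wrong baseline, nor extended to all focal-therapy patients, since the focal-alone share is unknown.

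Any effect on PFS or FFS is indirect and cannot be sized from the documents. No sample size or power figure changes. The rule matters for follow-up beyond 12 months, not for the feasibility analysis.

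**What to change.** In the focal therapy part of Protocol 5.9, date the first reference PSA at 12 months after completion of focal therapy (visit 4) instead of from randomisation, for all focal arms in CHRONOS-A and CHRONOS-B. The negative-MRI condition can stay. This gives the first-session rule the same time anchor as the second-session rule; the latter's biopsy condition need not be carried over. With T = 84 the value would fall at about day 449 (window 421 to 477), when both tests are already scheduled.

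The cost is one phrase in a protocol amendment, with no new sample, scan or visit.
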